13.5 Data Management

All cancer treatment related data, adverse events, and compliance with BR supplementation will be stored in the OnCore Data Management System of the Markey Cancer Center, as well as all strength measurements, body composition (CT and DXA), and quality of life surveys. Case report forms will record all study endpoints and data will be accessed in a secure manner using this password protected, encrypted software. The study statistician, along with staff from the Biostatistics Shared Resource Facility (BSRF), will work closely with the study PI and the MCC CRO staff on the development of eCRFs for the study. Instructions for data entry will be listed in Study-Specific Data Management Plan created by CRO staff in conjunction with the study statistician. The OnCore database is housed on secure servers maintained by the Cancer Research Informatics Shared Resource Facility (CRISRF) of Markey Cancer Center. The database is backed up daily.

Each subject will be assigned a sequence number at time of study entry through the OnCore system. This same sequence number will be distributed to study personnel at CCTS and utilized for all data. Data will be accessed by the study statistician via OnCore on a regularly scheduled basis to perform statistical programming to assess data quality control, study recruitment and to generate interim reports and analyses. In collaboration with the study team, procedures and timelines will be developed for data quality control, resolution of data queries, interim reporting and final data analysis.

REFERENCES

1. Society AC. Cancer Facts & Figures 2012.

APPENDIX A

PERFORMANCE STATUS CRITERIA

ECOG Performance Status Scale		Karnofsky Performance Scale	
Grade	Descriptions	Percent	Description
0	Normal activity. Fully active, able to carry on all pre-disease performance without restriction.	100	Normal, no complaints, no evidence of disease.
		90	Able to carry on normal activity; minor signs or symptoms of disease.
1	Symptoms, but ambulatory. Restricted in physically strenuous activity, but ambulatory and able to carry out work of a light or sedentary nature (e.g., light housework, office work).	80	Normal activity with effort; some signs or symptoms of disease.
		70	Cares for self, unable to carry on normal activity or to do active work.
2	In bed <50% of the time. Ambulatory and capable of all self-care, but unable to carry out any work activities. Up and about more than 50% of waking hours.	60	Requires occasional assistance, but is able to care for most of his/her needs.
		50	Requires considerable assistance and frequent medical care.
3	In bed >50% of the time. Capable of only limited self-care, confined to bed or chair more than 50% of waking hours.	40	Disabled, requires special care and assistance.
		30	Severely disabled, hospitalization indicated. Death not imminent.
4	100% bedridden. Completely disabled. Cannot carry on any self-care. Totally confined to bed or chair.	20	Very sick, hospitalization indicated. Death not imminent.
		10	Moribund, fatal processes progressing rapidly.
5	Dead.	0	Dead.

APPENDIX B

CTCAE version 4.0:

http://ctep.cancer.gov/protocolDevelopment/electronic_applications/ctc.htm

APPENDIX C

Patient Name: _____
Patient ID#: _____
Date Range: ____/____/____ to ____/____/____

Weekly Supplement Log

Instructions for the participant: This is a weekly log on which you are to record each supplement dose you take. For each dose write down the day, time and amount consumed (only fill out if supplement is mixed with water). Bring the log and all supplement packaging with you to your next scheduled supply pick-up.

Dose Number	Day (Example: Monday)	Time (Example: 12:00pm)	Amount Consumed (percent drank: 50%, 100%)	How was it taken (mouth or tube)
1				
2				
3				
4				
5				

Did you vomit up your supplement within 15 minutes of taking it on any day? If yes, how many days? _____

Did you retake the supplement each time? If yes, how many times did you retake it? _____

Patient Initials: _____

Date: _____

Section to be completed by research personnel:

Distribution Date: ____/____/____

Return Date: ____/____/____

Total Bags Returned: _____

Number of Empty Bags: _____

Comments: _____

Signature (Research Personnel)

Date

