1.2 Secondary Objectives

- Quantify changes in strength, and body composition, before and following supplementation
- Determine feasibility of beetroot supplementation in head and neck cancer patients defined for each patient as the proportion of days successfully consumed supplement during treatment schedule
- Determine the toxicity of concentrated beetroot given in conjunction with radiation or chemo-radiation in SCCHN as measured by CTCAE v. 4.0
- Evaluate the trend in grade of mucositis during radiotherapy or chemoradiotherapy as measured weekly by CTCAE v 4.0
- Determine 1- and 2-year locoregional control rate and progression-free survival of subjects enrolled on this clinical trial.

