5.1.3 Beetroot Administration

Study Supplements:

Subjects will be given 10 grams of concentrated organic beetroot crystals to mix with 120ml of water (BEETELITETM). Beetelite study supplement readily dissolve in water and may be given via gastrostomy tube or orally.

Daily Supplement Administration:

Subjects will begin daily supplementation following baseline measures (1-2 weeks before 7-week IMRT and for a minimum of 4 days) and will continue supplementation 4-6 weeks after treatment. Patients will be taught to self-administer their assigned study beverage by mouth and via PEG (as needed) by study staff during the baseline measurement period for the entirety of the trial. Patients requiring enteral support will be taught how to self-administer their assigned study beverage by a CRA or CRN. Compliance will be monitored by verbal assessment at clinic visits and by collection of written logs. Written instructions (Appendices E and F) for proper mixing of study beverage powders with water will be provided to both study volunteers and MCC staff involved in supplement administration and supervision. MCC staff will supervise the initial self-administration to ensure uniformity of ingestion. Subjects will be required to record the supplement intake in a dietary log which will be reviewed frequently at clinic visits.

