Study volunteers will be asked to retain all used and unused study packaging on a weekly basis to turn in to study staff at the end of the week. Study packaging will be compared to the patient generated compliance log to document weekly compliance data. Subjects who are deemed "non-compliant" with the beetroot protocol (less than 3 consumed supplements during any 1 week period between baseline and midpoint measures) will be excluded in the per protocol analysis. Compliance to beet root consumption between midpoint and endpoint measure will be encouraged with weekly phone calls by nutrition graduate students supervised by [name]. [name] will oversee all aspects of the supplementation protocol. The Investigational Drug Service (IDS) at the University of Kentucky will assist with storage, supply management, quality control, and transfer of all beet root.

Bulleted supplementation administration guidelines for each study period are provided below: Baseline and prior to IMRT enrollment (supplement initiation period):

- Following randomization, participants will be taught to self-administer their supplement by study personnel.

- The CRA or nutrition student will then distribute the supplement needed for the 1-2 weeks prior to IMRT to the participant.
- The supplement powder will be packaged in 10g portions by the IDS. Packaging will only be identified by the letter “A” or “B” and only IDS staff will be unmasked to supplement assignment.
- Participants will begin daily, single dose supplementation (M-F during the afternoon hours) on the first day of receiving their supplement from study personnel.
- Participants will be taught to mix their assigned powder with 120mL of water and self-administer within 30 minutes of mixing.
- Compliance during this time period will be encouraged by phone calls, a supplement “count,” and with a patient generated supplement log sheet.

7-8 week IMRT treatment period (daily supplement observation period):

- Participants will be asked to continue daily (M-F) self-administration of the supplement. The pre-measured supplement powder will be provided to the participant on a weekly basis and patients will be asked to consume the supplement during the afternoon hours (M-F).
- At the beginning of treatment and throughout the IMRT period, study personnel will assess the need to provide additional education on proper self-administration of the study supplement (ex. Transitioning from PO feeding to enteral feeds).

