- CRNs serving as study personnel may offer observation or administration assistance if patient requests this and may document supplement compliance.
- Patients will be instructed to make up any missed doses by taking up to 1 additional dose per day on the weekend days. Patients will receive 5 doses per week (for M-F) and will be instructed to never exceed 1 dose per day.

4-6 weeks post-IMRT (discharge period):

- After completion of IMRT the participant will be instructed to continue daily (M-F) self-administration (PO or PEG) until completion of endpoint measures.
- For patients requiring supplement administration assistance at discharge, a family member or caregiver will be identified and taught to provide assistance.
- On the day of discharge and during scheduled follow-up visits, the CRA will distribute the pre-measured supplement packets needed for daily administration.
- Participants will continue to follow the supplement mixing protocol and be reminded to consume their assigned supplement within 30-minutes of mixing.
- Supplement compliance will continue to be encouraged by weekly phone calls by study personnel and compliance logs/supplement counts will occur at least twice per month.

Supplementation on Testing Days

On testing days, The BEETELITE™ solution (beet root) will be administered on-campus 20-45 minutes before subjects undergo the baseline, midpoint (following IMRT), and endpoint (4-6 weeks following midpoint) strength/endurance measures. Prior to testing, subjects will not have to refrain from standard oral care, using antibacterial mouth wash, or chewing gum 48 hours before testing sessions because the BEETELITE™ product does not rely on salivation/oral bacteria to convert dietary nitrate to nitrite (23). Previous studies have administered up to 500mL of beet root per day with nitrate concentrations of 5.5 mMol (24), 6.2mMol (7, 25), 5.2mMol (26), and 5.1mMol (27). Plasma nitrite (NO_2^-) levels in these aforementioned studies also increased following dietary nitrate supplementation.

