11. MEASUREMENT OF EFFECT

11.1 Toxicity

For the purposes of this study, patients receiving beetroot supplement will be re-evaluated for toxicity as listed above and weekly during radiation as per institutional standard. All subjects receiving beetroot supplement will be evaluated for toxicity from the time of their first treatment with beet root to the end of study. Subjects will also be required to record each dose of beet root juice, including date and time, and subjective side effects (i.e. nausea, diarrhea, allergic reactions) noted after each dose. Subjects receiving only muscle strength testing will not be followed for toxicity as they receive standard of care and supportive medications as per routine. These subjects are not considered to be part of the interventional study but certainly serve as a baseline observational cohort.

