APPENDIX D

Patient Name: _____

Patient ID#: _____

Date Range: ____/____/____ to ____/____/____

Monthly Supplement Log

Instructions for the participant: This is a monthly log on which you are to record each supplement dose you take. For each dose write down the dose number, time and amount consumed as a percent (only write down if supplement is mixed with water) under the day you had it. For example, write down: Dose 1, 12pm and 50% if you drank half of the supplement. Bring the log and all supplement packaging with you to your next scheduled supply pick-up.

Sunday	Monday	Tuesday	Wednesday	Thursday	Friday	Saturday
 Mouth  Tube						
 Mouth  Tube						
 Mouth  Tube						
 Mouth  Tube						
 Mouth  Tube						

Did you vomit up your supplement within 15 minutes of taking it on any day? If so, how many days?

Did you retake the supplement each time? If not, how many times did you retake it? _____

Patient Initials: _____

Date: _____

Section to be completed by research personnel:

Distribution Date: ____/____/____

Return Date: ____/____/____

Total Bags Returned: _____

Number of Empty Bags: _____

Comments: _____

Signature (Research Personnel)

Date

Beetroot Juice Supplement Instruction Sheet (by stomach tube)

1. Mix the supplement powder with 4-8 oz of water only.
2. Do not mix the powder with anything other than water or more than 8 oz of water.
3. You may pour water into a glass and add in the powder or place the powder in a small bottle of water to pour in the tube.
4. Flush the tube with a small amount of water before and after administration of the supplement according to your physician's guidelines.
5. Pour the entire supplement within 2-3 minutes so it is all in the stomach at the same time.
6. On your supplement log write down the day (example: Monday), dose number (example: 1), approximate time you mixed the powder (example: 9:00am), and how much you administered (as a percent, example: 100%).
7. Administer the supplement between afternoon hours of 12-5pm.
8. The supplement is meant to be taken on weekdays (Monday-Friday).
9. If a dose is forgotten, take as soon as you remember that day. Then resume the supplement schedule the next day.

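### The weekly supplement log asks for the number of retaken doses only when the answer is already known, and no rule says how a vomited, unreplaced dose is counted

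*Combined protocol and SAP*

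**What the plan says.** Section 1.2 makes feasibility a secondary objective, defined for each patient as the "proportion of days successfully consumed supplement during treatment schedule". Section 5.1.3 takes a patient with fewer than three supplements consumed in any one week between baseline and midpoint out of the per-protocol analysis. Section 13.4.2 sets the matching requirement of at least three servings per week.

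The data come from several sources. Section 5.1.3 says: "Study packaging will be compared to the patient generated compliance log to document weekly compliance data". It also says: "Compliance will be monitored by verbal assessment at clinic visits and by collection of written logs". Research nurses "may document supplement compliance". Section 11.1 adds: "Subjects will also be required to record each dose of beet root juice, including date and time", together with subjective side effects.

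Both logs ask about vomiting once per form, not on each dose row. The weekly log asks: "Did you vomit up your supplement within 15 minutes of taking it on any day? If yes, how many days". The follow-up questions then differ:

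- Weekly log (Appendix C): "Did you retake the supplement each time? If yes, how many times did you retake it"
- Monthly log (Appendix D): "Did you retake the supplement each time? If not, how many times did you retake it"

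Section 5.1.3 permits one repeat on the same day when vomiting occurs within 15 minutes. It does not say how the original dose or its repeat enters the compliance count.

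**The concern.** The two forms collect the same item under opposite conditions. On the weekly log the count is requested when it adds nothing and skipped when it is needed.

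The counting rule is also missing. The protocol treats vomiting within 15 minutes as a distinct event, since only then may the dose be repeated. That distinction is not carried into the definition of feasibility or into the three-per-week rule. The amount column on the log records the percentage drunk, not the percentage kept. A dose that was drunk, vomited and not replaced can therefore leave a 100% entry and an empty packet.

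Two results are at stake: the feasibility proportion, and membership of the per-protocol set, where a single week below three is enough to remove a patient. The weekly log probably serves the radiotherapy period, because packets are supplied weekly then. That is an inference, as the documents do not assign the forms to periods. Vomiting is foreseeable, since section 5.1.2 describes high-dose cisplatin as highly emetogenic.

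**Working it through.** The plan states no figure for this item. The interval half-widths in section 13.2 (27.75, 22.85 and 17.7 points for n = 10, 15 and 25) reproduce with exact 90% limits as 27.76, 22.81 and 17.67. They concern the primary endpoint and do not depend on this point.

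**Inputs.** Five planned doses per week and a cut of three per week (section 5.1.3); the question wording in Appendices C and D.

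**Notation.** D = distinct days with a logged dose; V = days with vomiting within 15 minutes; R = vomited doses that were retaken, 0 ≤ R ≤ V; K = days with a retained dose. Assuming that every repeat was kept, which neither log asks,

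K = D − V + R.

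**What each log reveals about R**

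| Answer to 'each time?' | Weekly log | Monthly log |
|---|---|---|
| Yes | R = V; the number is asked but redundant | R = V; the number is not needed |
| No | number not asked; R is anywhere from 0 to V − 1 | number asked; R is known |

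The monthly log identifies R for every V. On the weekly log, 'no' with V = 1 gives R = 0. With V ≥ 2, R is not identified from these items.

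**Weekly log, D = 5, answer 'no'.** K runs from 5 − V (R = 0) to 5 − V + (V − 1) = 4.

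| V | K | Can K fall below 3? |
|---|---|---|
| 1 | 4 | no |
| 2 | 3 to 4 | no |
| 3 | 2 to 4 | yes |
| 4 | 1 to 4 | yes |
| 5 | 0 to 4 | yes |

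From V = 3 the range spans the per-protocol cut.

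**Can packets resolve it?** Let P be the number of packets used. If each dose and each repeat used one packet, and all packets were returned, R = P − D. Then K = D − V + (P − D) = P − V. For D = 5 and V = 3, P = 5 gives K = 2, P = 6 gives K = 3 and P = 7 gives K = 4. The form holds the empty-bag count and V, so the answer can often be recovered, but no section prescribes this calculation.

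**Size if vomited doses were counted as consumed.** The documents give no vomiting rate, so the frequencies here are assumptions. Over 7 weeks (35 weekday doses), each unreplaced dose moves one patient's feasibility by 1/35 = 2.9 points; over 8 weeks (40 doses), by 1/40 = 2.5 points. With 1, 2 or 3 unreplaced doses every week, a reported 100% would correspond to a retained 80%, 60% or 40% (4/5, 3/5, 2/5). One reclassified patient is 1/25 = 4% of the supplemented cohort.

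**The case against.** The strongest reply is that the information mostly exists. The log records vomiting days, dose days and empty bags. In a week with five packets, five dose days and three vomiting days, no packet was left for a repeat, so two retained days follow from the form itself. Section 5.1.3 mentions extra packets only at discharge and supplies five doses per week during treatment. Verbal assessment and nurse documentation add further sources, section 5.1.3 says vomiting will be closely monitored, and section 11.1 calls for side effects after each dose. Section 13.5 places data-entry instructions in a data management plan that is not among the documents.

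Much of this stands. It narrows the loss to weeks with two or more vomiting days, the answer 'no', and packet counts that are incomplete or not reconciled. It does not remove the point. No section tells anyone to derive retakes from packets, the side-effect record has no column on the dose rows of the weekly log, and no source is given a rule for adjusting the count.

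A reader might infer three stronger things, none of which the documents support:

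- **That vomited, unreplaced doses are counted as consumed.** No section says so, and the word 'successfully' can be read as excluding them. The gap is an unstated rule.
- **That compliance rests on log and packets alone.** Section 5.1.3 names other sources.
- **That the monthly log is faulty as well.** Together with the vomiting days, its wording gives the number unreplaced in every case.

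Nor do the documents show that feasibility is overstated among cisplatin patients. Section 13.2 expects only 10 of 25 supplemented patients to receive chemoradiation, section 5.1.2 allows cetuximab for some, and no vomiting frequency is given for either.

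**Conclusion.** The point holds in a limited form. The weekly log's follow-up question is conditioned the wrong way round and conflicts with the monthly log. It leaves the number of retakes unasked when vomiting occurred on two or more days and not all doses were retaken. From three vomiting days in a five-dose week, the uncertainty reaches across the per-protocol cut unless packets and dose days are reconciled.

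Separately, the plan does not define whether a vomited, unreplaced dose is successfully consumed. Such doses may therefore be counted, and feasibility may be overstated. The amount cannot be stated without a vomiting rate; the percentages above are illustrations. They assume that all repeats were kept and consider only vomiting within 15 minutes, which is all the logs ask about.

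The effect is confined to a descriptive secondary endpoint and a supplementary analysis set. The primary treatment-compliance estimate in all patients does not change. The correction is still worth making before data collection, because an item that was never asked may not be recoverable.

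**What to change.** 1. In Appendix C, change 'If yes' to 'If not' so that it matches Appendix D, or ask for the number retaken whatever the answer. Either makes R known for every V.
2. Preferably, replace the summary questions with two tick boxes on each dose row, one for vomiting within 15 minutes and one for a retaken dose. This ties the event to a day. The second box should be ticked only if the repeat was kept, so that the rule below can be applied.
3. In sections 5.1.3 and 13.4.2, state that, for counting purposes only, a day is successfully consumed if the dose or its repeat was not vomited within 15 minutes. Apply the same rule to feasibility and to the three-per-week per-protocol cut. This concerns the analysis and leaves the administration instructions as they are.

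The cost is a form revision and a sentence of counting-rule text in each of the two sections. The reported feasibility figure may be slightly lower.

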APPENDIX D

Patient Name: _____

Patient ID#: _____

Date Range: ____/____/____ to ____/____/____

Monthly Supplement Log

Instructions for the participant: This is a monthly log on which you are to record each supplement dose you take. For each dose write down the dose number, time and amount consumed as a percent (only write down if supplement is mixed with water) under the day you had it. For example, write down: Dose 1, 12pm and 50% if you drank half of the supplement. Bring the log and all supplement packaging with you to your next scheduled supply pick-up.

Sunday	Monday	Tuesday	Wednesday	Thursday	Friday	Saturday
 Mouth  Tube						
 Mouth  Tube						
 Mouth  Tube						
 Mouth  Tube						
 Mouth  Tube						

Did you vomit up your supplement within 15 minutes of taking it on any day? If so, how many days?

Did you retake the supplement each time? If not, how many times did you retake it? _____

Patient Initials: _____

Date: _____

Section to be completed by research personnel:

Distribution Date: ____/____/____

Return Date: ____/____/____

Total Bags Returned: _____

Number of Empty Bags: _____

Comments: _____

Signature (Research Personnel)

Date

Beetroot Juice Supplement Instruction Sheet (by stomach tube)

1. Mix the supplement powder with 4-8 oz of water only.
2. Do not mix the powder with anything other than water or more than 8 oz of water.
3. You may pour water into a glass and add in the powder or place the powder in a small bottle of water to pour in the tube.
4. Flush the tube with a small amount of water before and after administration of the supplement according to your physician's guidelines.
5. Pour the entire supplement within 2-3 minutes so it is all in the stomach at the same time.
6. On your supplement log write down the day (example: Monday), dose number (example: 1), approximate time you mixed the powder (example: 9:00am), and how much you administered (as a percent, example: 100%).
7. Administer the supplement between afternoon hours of 12-5pm.
8. The supplement is meant to be taken on weekdays (Monday-Friday).
9. If a dose is forgotten, take as soon as you remember that day. Then resume the supplement schedule the next day.
10. Do not consume more than 1 dose in 1 day. However, if you vomit the dose within 15 minutes of putting it in your PEG tube, you may repeat the dose once that day (after recovering from vomiting and nausea).
11. If 1 dose is missed during the week, you can take the missed dose on Saturday.
12. If 2 doses are missed, you can take them on Saturday and Sunday.

Beetroot Juice Supplement Instruction Sheet (by mouth)

1. Mix the supplement powder with 4-8 oz of water only.
2. Do not mix the powder with anything other than water or more than 8 oz of water.
3. You may pour water into a glass and add in the powder or place the powder in a small bottle of water to drink.
4. Swallow as fast as possible within 2-3 minutes so it is all in the stomach at the same time.
5. On your supplement log write down the day (example: Monday), dose number (example: 1), approximate time you mixed the powder (example: 9:00am), and how much you drank (as a percent, example: 100%).
6. Consume the supplement between the afternoon hours of 12 and 5pm.
7. The supplement is meant to be taken on weekdays (Monday-Friday).
8. If a dose is forgotten, take as soon as you remember that day. Then resume the supplement schedule the next day.
9. Do not consume more than 1 dose in 1 day. However, if you vomit the dose within 15 minutes of swallowing it, you may repeat the dose once that day (after recovering from vomiting and nausea).
10. If 1 dose is missed during the week, you can take the missed dose on Saturday.
11. If 2 doses are missed, you can take them on Saturday and Sunday.

APENDIX G

Mucositis scoring

PROTOCOL ID: IDR-OM-01					
Site Number: _____	Subject ID Number: _____	Assessment Date: _____	/	/	/
D	D	M	M	M	Y
Assessment Type (mark only one):  Baseline  IMRT Visit, Week _____ Visit _____  End of Treatment (EOT)					
 Post-IMRT Week _____  Initial Follow-up (IFU)					
Oral Evaluator Initials: _____	Oral Evaluator Signature: _____				

Missed Visit Reason: _____

MUCOSITIS ASSESSMENT WORKSHEET

YES NO

Confirm that all PROs were completed prior to conducting this clinical exam.

DIET ASSESSMENT		
DIET 1: What has the subject been able to eat within the past 24 hours (mark only one):  Solids  Liquids  Nothing by mouth If Solids is marked above, proceed to the Mouth Pain Assessment. If Liquids or Nothing by Mouth is marked above, continue to DIET 2.	DIET 2: If the subject has been unable to eat Solid food, mark the reason(s) why (mark all that apply):  Nausea/Vomiting  Oral Discomfort  Loss of Appetite  Dry Mouth  Throat Discomfort  No teeth  Difficulty swallowing  Other: If Oral Discomfort is marked above, proceed to the Mouth Pain Assessment. If Oral Discomfort is NOT marked, continue to DIET 3.	DIET 3: Based solely on how the mouth feels, what does the subject feel (s)he could try to eat if (s)he did not have to swallow (mark only one):  Solids  Liquids  Nothing by mouth Proceed to the Mouth Pain Assessment.

MOUTH PAIN ASSESSMENT

Please indicate if the subject is experiencing any mouth pain or oral discomfort at this time: Yes OR No

ORAL ASSESSMENT

Oral Site	Ulceration/ Pseudomembrane Formation	Other Ulceration (e.g., tumor or surgical)	Erythema
Upper Lip	Yes  No  NE 	Yes  No  NE 	Yes  No  NE 
Lower Lip	Yes  No  NE 	Yes  No  NE 	Yes  No  NE 
Right Cheek	Yes  No  NE 	Yes  No  NE 	Yes  No  NE 
Left Cheek	Yes  No  NE 	Yes  No  NE 	Yes  No  NE 
Right Ventral & Lateral Tongue	Yes  No  NE 	Yes  No  NE 	Yes  No  NE 
Left Ventral & Lateral Tongue	Yes  No  NE 	Yes  No  NE 	Yes  No  NE 
Floor of the Mouth	Yes  No  NE 	Yes  No  NE 	Yes  No  NE 
Soft Palate	Yes  No  NE 	Yes  No  NE 	Yes  No  NE 

WHO Score (mark only one): Note: The Other Ulceration column will not be used when deriving the WHO Score

- WHO = 0 – None
- WHO = 1 – Erythema and Mouth Pain
- WHO = 2 – Ulceration/Pseudomembrane Formation; Able to eat Solids or could try to eat Solids if swallowing were not required.
- WHO = 3 – Ulceration/Pseudomembrane Formation; Able to eat Liquids or could try to eat Liquids if swallowing were not required.
- WHO = 4 – Ulceration/Pseudomembrane Formation; Unable to eat Solids or Liquids

Version Date 17-Oct-13

EMAIL TO CAP at [contact]

Confidential

Page 1 of 1
